1. Create a data set, one for each treatment group, of subjects with observed values and those needing estimation by MCMC. The missing PASI values in each data set will be filled in using the MCMC method with a total of 75 sets of imputation being performed. The seed used for these imputations will be 958 (Note: All other multiple imputation procedures described in this SAP will use this same seed as well). The procedure will sequentially estimate an imputation model for the PASI score at each post-Baseline visit (up to Week 16) where PASI is collected, with prior biologic exposure, and Baseline score as predictors. Note that PASI scores at earlier visits will also be used as predictors for the model of PASI at later visits. The resulting data sets for each treatment arm will be combined into one complete data set based on each of the 75 imputations.

Note: If one treatment group is complete, so without any missing values, then this treatment group is excluded from MCMC imputation and the observed data will be duplicated 75 times and rejoined to the imputed data set.

Note: The imputation model based on the MCMC method will only allow continuous variables as predictors. Therefore, prior biologic exposure will be re-coded as indicator variables (with values of 0 or 1). Because prior biologic exposure has just 2 levels, only one indicator variable will be needed.

2. For each complete imputed data set, the dichotomous responder rate based on the PASI scores will be computed. Each complete imputed data set will then be analyzed based on a logistic regression model with factors of treatment group and prior biologic exposure (yes/no).

Note: For derivation of PASI75 response, the imputed PASI value will be compared directly to the observed Baseline PASI value to determine whether or not a reduction of at least 75% was achieved. If values outside of the pre-defined range of values for PASI (0-72) are imputed, they will be cut off as appropriate after the multiple imputation procedure but before deriving the responder variables. For example an imputed PASI value of -0.5 would be changed to 0 before deriving the PASI75 responder variable.

3. The Week 16 results from the logistic regression analysis of each of the 75 imputed data sets will be combined into a single inference using SAS PROC MIANALYZE.

Some key points to consider relative to the calculation of the odds ratios and corresponding confidence intervals are noted below:

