A subject will be classified as a responder at Week 16 if they achieve a PGA score of 0 ('Clear') or 1 ('Almost clear') and they have at least a 2-category improvement relative to Baseline. Note that a PGA score of at least 3 is required per the inclusion criteria, so all subjects achieving a PGA score of 0 or 1 should, by definition, be a responder. However, in the case that a subject with a Baseline score of 2 is mistakenly randomized, then this subject may be classified as a responder only if a PGA score of 0 is achieved (thereby achieving the required 2-category improvement).

PGA response at Week 16 will be analyzed for treatment effects using pairwise comparisons based on the same method as that for the primary efficacy variable.

The MCMC algorithm is based on the multivariate normal model; imputed values for PGA will not generally be one of the discrete values actually used in PGA scoring (0, 1, 2, 3, or 4). Therefore, standard rounding rules will be applied to the imputed values in order to derive the

binary PGA response variable. For example, if a subject has a PGA score imputed as 1.4 (and assuming a Baseline PGA score of 3), this imputed value would be rounded down to 1, and the minimum change from Baseline of 2 would have been met. Therefore, this subject would be considered a responder.

The significance testing of each CZP treatment group vs PBO will be part of the fixed sequential testing procedure described in [Section 4.5](#).

8.2.2 PASI90 at Week 16

PASI90 response at Week 16 will be analyzed for treatment effects using pairwise comparisons based on the same method as that for the primary efficacy variable. Each CZP dose will be compared against placebo to establish superiority over placebo and will be tested at a significance level of 0.025 as part of the fixed sequence testing procedure outlined in [Section 4.5](#).

8.2.3 Change from Baseline in DLQI at Week 16

The Dermatology Life Quality Index (DLQI) is a skin-disease-specific questionnaire evaluating how symptoms and treatment affect patients' Health-Related Quality of Life (HRQoL). This instrument includes 10-questions that cover 6 domains including symptoms and feelings, daily activities, leisure, work and school, personal relationships, and treatment, as assessed over the past week. It is validated and reproducible in PSO patients.

The scoring of each answer for the DLQI is as follows:

Table 8–2: DLQI scoring

Response	Score
Very much	3
A lot	2
A little	1
Not at all	0

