8.3.1 PASI50, PASI75, PASI90, and PASI100 by Visit

See Section 8.1.1 for details of the derivation.

Initial Period

PASI50, PASI75, PASI90 and PASI100 responder rates will be summarized by randomized treatment group for the FAS at each time point (Weeks 2, 4, 8, 12 and 16). A comparison between treatment groups will be made at each time point using the same model and approach for handling missing data as described for the primary analysis. The estimate for the responder rate, the odds ratio, 95% CI, and p-value from the model will be presented. Additionally, the responder rates based on the observed data will be summarized using counts and percentages. Each time point will be analyzed separately. If the model fails, percentages for the responders and the corresponding 95% CIs will be displayed. If convergence is not obtained due to lack of responders in one or more treatment groups, methods described in Section 8.1.2 will be applied instead. For EPS only descriptive statistics will be provided.

Line plots will be generated to present PASI50, PASI75, PASI90 and PASI100 responder rates (as derived by the above procedure) by randomized treatment group through Week 16.

Blinded Maintenance Period (Interim Analysis, excluding subjects who escaped at Week 16)

The summaries will include the observed responder rates at each visit. Subjects who meet the criterion for escape (ie, not achieving PASI50 response) at Week 16 are excluded from the point of escape.

For other missing data, multiple imputation will be performed based on MCMC methodology. The analysis (logistic regression) of response rate on MCMC imputed data is similar to the procedure outlined in Section 8.1.2 except that escape subjects are not considered here. The estimated responder rates and corresponding 95% confidence intervals for the difference in proportion of responder vs. PBO and odds ratios vs PBO with 95% confidence interval and p-value at each visit will be presented by blinded maintenance treatment group based on the FAS.

Additionally, NRI will be used for imputation of missing data. The estimated responder rates, odds ratios vs PBO with corresponding 95% confidence interval and p-value at each visit in

the Blinded Maintenance Period [ie, Week 16 through Week 24] will be presented by blinded maintenance treatment group based on the FAS.

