PASI50, PASI75, PASI90 and PASI100 responder rates (based on simple counts and percentages only) will be also summarized for the Blinded Maintenance Period (Week 16 through Week 24) by blinded maintenance treatment group (combined group inclusive) using NRI imputed and observed data.

A table summarizing the (exact) logistic regression analysis results of PASI75/PASI90 response rates during Blinded Maintenance Period based on the subset of PASI75/PASI90 responders at Week 16 will also be provided (observed case, NRI and MCMC imputed data), procedure as outlined in [Section 8.1.2](#). Additionally, the same table will be produced to summarize simple counts and percentages using the blinded maintenance treatment groups (combined group inclusive) based on NRI and observed data only.

Line plots will be generated to present the percentages of responders over time by blinded maintenance treatment group (Blinded Maintenance Period treatment) over time (from Week 16 to Week 24) based on MCMC imputed data.

Maintenance Period (Final Analysis, including subjects who escaped after Week 16)

The analysis of the PASI50, PASI75, PASI90, and PASI100 responder rate during the Maintenance Period will be based on the BM FAS. Missing data will be handled based on a combination of NRI and multiple imputation. The procedure is described below:

1. Identify subjects who met the escape criterion at any timepoint (ie, did not achieve a PASI50 response), and do not include them in the multiple imputation model described in Step 2.
2. For all subjects not identified in Step 1, create a data set, one for each treatment group, of subjects with observed values and those needing estimation by multiple imputation. The missing PASI values in each data set will be filled in using the MCMC method with a total of 75 sets of imputations being performed. The procedure will sequentially estimate an imputation model for the PASI score at each post-Baseline visit where PASI is collected, with prior biologic exposure and Baseline score as predictors. The resulting data sets for each treatment arm will be combined into one complete data set based on each of the 75 imputations.

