3. For the subjects meeting the escape criterion identified in Step 1, all visits after the point of escape will be imputed via NRI. This imputation is based on meeting the escape criterion, whether or not the subject actually received escape treatment. Once imputation has been performed for these subjects, these records are duplicated 75 times and combined with the 75 imputations performed in Step 2.

Note: If subjects identified here have intermittent missing data at earlier time points, those will be imputed via NRI.

4. For each complete imputed data set, the dichotomous PASI responder rate based on the PASI scores will be computed. Each complete imputed data set will then be analyzed using simple proportions by treatment group ($p=x/N$, where x is the number of responder and N the number of subjects in this treatment group). The corresponding standard error for the sample proportion will be calculated with the square root of $p(1-p)/N$.

Note: For derivation of PASI75 response, the imputed PASI value will be compared directly to the observed Baseline PASI value to determine whether or not a reduction of at least 50% (or 75%, 90%, 100%) was achieved. If values outside of the pre-defined range

of values for PASI (0-72) are imputed, they will be cut off as appropriate after the multiple imputation procedure but before deriving the responder variables. For example, an imputed PASI value of -0.5 would be changed to 0 before deriving the PASI responder variable.

5. The results at each week of each of the 75 imputed data sets will be combined into a single inference using SAS PROC MIANALYZE.

The estimated responder rates at each week will be presented by treatment group based on the FAS.

Additionally, NRI will be used for imputation of missing data. Simple proportions will be calculated to estimate responder rates at each visit in the Maintenance Period (ie, Week 16 through Week 52). Responder rates based on observed case data will also be summarized.

A table summarizing the PASI75/PASI90 response rates (simple proportions) during Maintenance Period based on the subset of PASI75/PASI90 responders at Week 16 will also be provided (observed case, NRI and MCMC imputed data).

Line plots will be generated to present the percentages of responders over time by maintenance treatment group over time (from Week 16 to Week 52) based on MCMC imputed data.

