8.3.4 PGA score distribution

See Section 8.2.1 for details of the derivation. The summaries described in this section are based on observed data – no imputation will be performed.

Initial Period

The distribution of the PGA score (0, 1, 2, 3, or 4) will be summarized in shift tables comparing the change from Baseline versus post-Baseline (Weeks 2, 4, 8, 12 and 16) by randomized treatment group for the FAS and EPS. The shift tables will be provided for each time point.

Maintenance Period

The distribution of the PGA Score will be summarized in shift tables comparing the change from Baseline versus post-Baseline (Weeks 16, 20, 24, 28, 32, 36, 40, 44, 48 and 52) by blinded maintenance or escape maintenance treatment group for the FAS and by maintenance treatment group for EPS. The shift tables will be provided for each time point.

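### Maintenance imputation (SAP 8.3.1) drops everyone who ever escapes, treats the same gap in two ways, and specifies a model that may not be fittable for PBO/PBO

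*SAP*

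**What the plan says.** SAP 8.3.1, final analysis of the Maintenance Period, combines non-responder imputation (NRI) with multiple imputation.

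- **Step 1** finds all subjects who met the escape criterion at any timepoint and says "do not include them in the multiple imputation model described in Step 2".
- **Step 2**, for everyone else, is to "create a data set, one for each treatment group, of subjects with observed values and those needing estimation by multiple imputation". It then fits "an imputation model for the PASI score at each post-Baseline visit where PASI is collected, with prior biologic exposure and Baseline score as predictors".
- **Step 3** sets an escaper's visits after escape to non-response and puts the subject back in the denominator. A note adds: "If subjects identified here have intermittent missing data at earlier time points, those will be imputed via NRI".

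SAP 8.3.2 applies the same method to PGA response.

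Three other places bear on this. SAP 4.2 makes escapers non-responders only from escape onwards and assigns the remaining missing PASI and PGA data to MCMC imputation. SAP 8.1.2, for the primary analysis, states that "PASI scores at earlier visits will also be used as predictors for the model of PASI at later visits" and lets a treatment group with no missing values skip MCMC; 8.3.1 repeats neither statement. SAP 8.2.1 notes that "The MCMC algorithm is based on the multivariate normal model".

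NRI and observed-case rates are also reported. The Week 16 to 52 line plots use the MCMC data only. Neither 8.1.2 nor 8.3.1 gives a fallback for a group whose imputation model cannot be fitted.

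**The concern.** There are three separate problems.

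1. **Selection on a later outcome.** A subject who withdraws at Week 26 might have failed PASI50 at Week 32 or 40. Step 1 removes the subjects who did fail there, including their valid scores from before escape. What remains over-represents sustained response.
2. **Unequal handling of gaps.** How a missed visit is treated depends on what the subject does later, and 8.3.1 and 4.2 give different answers for the same missing value.
3. **Model size and specification.** A separate joint model over all visits may have more variables than a small group has subjects, and Step 2 leaves open whether earlier PASI enters the model at all.

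Durability of response is a secondary objective and a stated purpose of the final analysis (SAP 4.3), so these rates and plots will be read closely even though they are descriptive.

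**Working it through.** **The plan's own figures.** The SAP gives no group size for this imputation. The only related figures are the Week 16 power statements in protocol 14.8.1, and they reproduce. For 70% against 15% at two-sided 0.025, 43 against 22 gives 99.3% (pooled z) or 98.6% (Fisher), against a stated minimum of 98%. With 50 against 25 the results are 99.8% and 99.3%, against a stated >99%.

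**Number of variables, if earlier visits are predictors.** The Initial Period has PASI "at each time point (Weeks 2, 4, 8, 12 and 16": 5 visits. The Maintenance Period visits are "Weeks 16, 20, 24, 28, 32, 36, 40, 44, 48 and 52" (listed for PGA; protocol Section 8 has PASI at the same visits): 9 after Week 16. So 5 + 9 = 14 post-Baseline scores, plus Baseline PASI and prior biologic exposure = 16 variables. The unrestricted normal model has 16 means and 16 × 17 / 2 = 136 variances and covariances, 152 parameters in all.

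**Subjects needed.** A sample covariance matrix from n subjects has rank at most n − 1, so full rank for 16 variables needs n ≥ 17. With 4, 8 or 12 subjects the rank is 3, 7 or 11. The usual inverse-Wishart draw with n − 1 degrees of freedom is undefined at n ≤ 16.

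**Subjects available.**

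- *PBO/PBO.* SAP Section 8 expects a majority of the 25 placebo subjects to switch to CZP. That means at least 13, so at most 12 never escape. As a cross-check, with an assumed Week 16 PASI50 rate p, P(at least 17 of 25 respond) is 3 × 10⁻⁹ at p = 15%, 0.0001 at 30%, 0.004 at 40% and 0.05 at 50%, before any later escape.
- *Each re-randomised CZP 200mg arm.* Assume 80% to 90% PASI50 at Week 16 and 10% later escape. The expected number of never-escapers is 50 × 0.8 × 0.5 × 0.9 = 18.0 to 50 × 0.9 × 0.5 × 0.9 = 20.25. P(at least 17) is 0.67 to 0.86, from Bin(50, 0.36) and Bin(50, 0.405). If the 1:1 split is exact, Bin(20, 0.9) gives 0.87 at the lower rate. These arms are borderline.
- *CZP 400mg Q2W.* Between 35 and 50 subjects before later escapes, so the model can be fitted.

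**Chance that the problem arises in PBO/PBO.** If the 8.1.2 skip rule carries over, MCMC is needed only when the group has a missing value. With 4 to 8 never-escapers and an assumed 10% dropout, P(no missing value) is 0.9⁴ = 0.66 to 0.9⁸ = 0.43. The problem then arises with probability 0.34 to 0.57, before intermittent gaps are counted.

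**Size of the selection effect.** A large-sample simulation (N = 60,000) separates selection from the small-group problem. It compares imputation from never-escapers with imputation that keeps pre-escape PASI and applies the escape rule to imputed values. Trajectories, escape and dropout are assumed, because the documents give none. Week 52 PASI50 in three of the scenarios, with dropout depending on observed PASI:

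| Scenario (nominal dropout) | Later escape | Overall: truth / SAP / alternative | Among dropouts: truth / SAP / alternative |
|---|---|---|---|
| CZP (10%) | 7.2% | 85.2 / 85.4 / 85.2 | 86.0 / 89.3 / 85.7 |
| CZP, more loss of response (20%) | 14.4% | 73.1 / 73.9 / 72.7 | 76.4 / 81.1 / 73.8 |
| PBO (20%) | 62.3% | 4.6 / 5.4 / 4.5 | 45.7 / 75.3 / 42.1 |

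Across all CZP scenarios, the SAP method exceeds the true PASI50 rate by 0.2 to 1.0 points overall and by about 3 to 6 points among dropouts. The alternative lowers the SAP's overall figure by 0.2 to 1.5 points. For PASI75 the SAP's overall error runs from −1.0 to +0.5 points, negative when PASI was skewed. PASI90 changes by 0.2 points or less.

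**Gaps, section against section.** Two subjects miss Week 20. One escapes at Week 40; the other never does. Under the Step 3 note the first is a non-responder at Week 20 and the second is multiply imputed. Under 4.2 both are multiply imputed, because Week 20 precedes escape. No assumption about rates is needed.

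**The case against.** The strongest reply is that the existing rules already limit the optimism.

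- Escapers count as non-responders after escape, whether or not they took escape treatment.
- PASI is taken at early withdrawal and mapped to the next scheduled visit, so some failing dropouts are caught by the criterion and never imputed.
- The note on gaps lowers the rates.
- A dropout's own partial data enter Step 2, so the donor data are not purely subjects who passed every check. Since escape is decided only at Weeks 16, 24, 32 and 40, a subject below PASI50 at another visit may stay in the model.

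All of this stands. It is why the overall effect is small, but it does not restore the discarded pre-escape scores.

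On fitting, Step 2 names only Baseline PASI and prior biologic exposure as predictors. Read literally, each visit has 3 coefficients and the model can be fitted. That reading avoids the singular matrix at the price of ignoring the withdrawn subject's own Week 16 and later PASI. Neither reading is satisfactory, and the SAP does not say which is meant.

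It can also be said that imputation by group matches the primary analysis, and that pooling would let CZP correlations drive the few placebo imputations. That is fair, and it is why sharing covariance is offered below only as one possible fallback.

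**Conclusion.** The point holds in a limited form. Removing ever-escapers selects the imputation data on a later outcome and tends to favour response, chiefly PASI50, among subjects who withdraw before meeting the criterion. In CZP groups the overall effect is about 1 point for PASI50, under assumed trajectories and dropout. The gap rule contradicts SAP 4.2 on its face. The model is either too large for PBO/PBO once a value is missing there, and borderline for the re-randomised CZP 200mg arms, or it ignores earlier PASI.

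Three stronger inferences are not supported.

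- *That the maintenance rates as a whole are biased upwards.* Escapers are counted as non-responders, their earlier gaps are handled conservatively, and the PASI75 error has no fixed sign.
- *That the procedure cannot run for PBO/PBO.* That needs both the 16-variable reading and a missing value in a never-escaper. Week 16 placebo escapers also sit in this group (SAP 3.5.9 and 3.6.1), with non-response set by rule after escape.
- *That this is the main durability analysis.* The SAP does not say so. The results are descriptive, NRI and observed-case rates stand beside them, and only the line plots rest on MCMC alone.

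No hypothesis test is affected. The change is worth making because following the text gives a poorer result on either reading and the repair is cheap.

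**What to change.** Revise Steps 1 to 3 of SAP 8.3.1, and 8.3.2 by reference:

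1. Keep escapers' PASI up to and including the escape visit in the imputation model, then set their later visits to non-response.
2. Apply the same non-response rule after any imputed value that fails PASI50 at an escape-check visit (Weeks 16, 24, 32, 40). Without this, imputed subjects are spared a rule that observed subjects face.
3. Impute pre-escape gaps the same way for all subjects, in line with 4.2, and delete the Step 3 note.
4. Name the predictors: Baseline PASI, prior biologic exposure, Week 16 and the one or two preceding visits. That is at most 5 predictors, or 6 coefficients with the intercept, per visit.
5. State whether a complete group skips MCMC, as in 8.1.2, and give a fallback for any group too small to fit, for example NRI or a model sharing covariance across groups.

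The cost is SAP wording and modest reprogramming. If covariance is shared, the analysis assumes common visit-to-visit correlation across groups, which is least secure for placebo.
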